APPENDIX 4. ALS Cognitive Behavioral Screen (ALS-CBS)

Patient Id: _____ DOB/Age: _____ Gender: _____
 Onset Date: _____ FVC: _____ Education: _____
 Onset Region: bulbar, arm, leg, trunk, respiratory (circle one)

Mark if patient responses were written, attach sheet

Attention

a) Commands: I am going to say some commands. Please listen carefully and then do what I say. (If patient is unable to indicate with finger, movement can be substituted with eyes, arm or other means).

Point/indicate (with your finger) to the ceiling and then to your left. # errors 0 1+

Touch your shoulder, point to the floor, and then make a fist. Score (circle) 1 0

b) Mental Addition/Language: I am going to say some phrases. I want you to tell me the number of syllables in each phrase. For example, "the table" has 3 syllables. (Repetition of each phrase is allowed once).

1. The weather is nice. (Correct response: 5) answer _____ # errors 0 1+

2. Tomorrow will be sunny. (Correct response: 7) answer ____ Score (circle) 1 0

(Score 0 if >20 seconds on either)

c) Eye Movements*: Saccades and Antisaccades.

of Correct Saccades out of 8: ____ /8 Score: 8/8 =1 points, ≤7/8 = 0 points

of Correct Antisaccades out of 8: ____ /8 Score: 8/8 =2 points, 7/8 = 1 points, ≤ 6/8 = 0 points

SCORE:	  / 5
---------------	---------------------

***Eye Movement Instructions**

Saccades: I am going to hold my fingers up. Please keep your head straight and look at me. When I wiggle a finger, I want you to look at that finger and then look back at me (examiner should execute this eye movement themselves to demonstrate). Look at my finger by moving your eyes only, trying to keep your head still. Each time I will wiggle a finger, look at it and then back to me (Do 2-3 trials with the patient as practice). We will do that a few times. Ready? (Do 8 random trials, pause for 1-2 seconds between each trial).

Antisaccades: Good, next I am going to wiggle a finger again, but this time, I want you to look AWAY from the finger that moves. For example, if I move this finger (wiggle one) then I want you to look at the other finger, not the one that moves, ok? (Examiner should demonstrate for patient) Let's try it (do 2-3 trials). Just like before, try to keep your head still and just move your eyes. After each one, look back at me. Ready? (Do 8 random trials, pause for 1-2 seconds between each trial).

Concentration

I am going to say some numbers. After I say them, I want you to say them to me backwards, or in reverse order. For example, if I say 3-6, you would say 6-3. (If written, do not allow patient to write forward span. Discontinue after failure on two consecutive trials).

	Correct	Incorrect		Correct	Incorrect
2-9 (9-2):			7-8-6-4 (4-6-8-7):		
6-4 (4-6):			5-4-1-9 (9-1-4-5):		
3-7-2 (2-7-3):			8-2-5-9-3 (3-9-5-2-8)		
5-8-1 (1-8-5):			5-7-6-3-9 (9-3-6-7-5):		

Maximum Span Correct (Enter score):	  / 5
--	---------------------

Tracking/Monitoring

d) Months: Please say the months of the year backwards, starting with December. (circle omissions/mark repetitions & intrusions)

Dec Nov Oct Sep Aug Jul Jun May Apr Mar Feb Jan

errors:

For 0 errors enter a score of 2 for this section.

For 1 error enter a score of 1 for this section.

For 2 or more errors enter a score of 0 for this section.

Score (enter):

e) Alphabet: Please say/write the alphabet for me. (mark uncorrected errors, omissions or intrusions)
errors 0 1+

A B C D E F G H I J K L M N O P Q R S T U V W X Y Z

Score (circle) 1 0

f) Alternation Task: I want you to alternate between numbers and letters, starting with 1-A, and then 2-B, 3-C, and so on. Please continue from there, alternating between number- letter, number- letter, in order, without skipping any until I tell you to stop. (Errors: Any mistake in sequencing, i.e., 7-H, or 8-9). # errors 0 1 2

4-D 5-E 6-F 7-G 8-H 9-I 10-J 11-K 12-L 13-M Score (circle) 2 1 0

SCORE:	/ 5
---------------	------------

Initiation and Retrieval

Say (write) as many words as you can starting with the letter F, as quickly as you can, in 1 minute. (Show patient Fluency Rules) You cannot say/write the names of people, places or numbers. Please do not say/write the same word with just a different ending, like truck, trucks. (S words can be substituted for F words). Errors: repetitions, rule violations

- FLUENCY RULES: NO NAMES OF PEOPLE
NO NAMES OF PLACES NO NUMBERS
DO NOT USE SAME WORD WITH DIFFERENT ENDING

- | | |
|-------|--------|
| i. | ii. |
| iii. | iv. |
| v. | vi. |
| vii. | viii. |
| ix. | x. |
| xi. | xii. |
| xiii. | xiv. |
| xv. | xvi. |
| xvii. | xviii. |
| xix. | xx. |

SCORE:	/ 5
---------------	------------

TOTAL SCORE:	/ 20
---------------------	-------------

ALS Caregiver Behavior Questionnaire

These questions pertain to possible changes in behavior that you have noticed since the onset of ALS symptoms. As best you can, consider changes that are unrelated to physical weakness. For example, question #1 asks about interest in activities. If the person can no longer play tennis but seems interested in it (i.e. talks about it, watches it on television), then you would circle 3 or no change in level of interest. If the person has always had the trait in question, please respond no change, since there has been no change seen over time.

Compared to before ALS onset, does he/she:

1. Have less interest in topic/events that used to be important to them?
 3 No change 2 Small Change 1 Medium Change 0 Large Change
2. Show little emotion, or seem less responsive emotionally?
 3 No change 2 Small Change 1 Medium Change 0 Large Change
3. Seem more agreeable or pleasant than in the past with fewer worries?
 3 No change 2 Small Change 1 Medium Change 0 Large Change
4. Fail to think things through before acting?
 3 No change 2 Small Change 1 Medium Change 0 Large Change
5. Seem more withdrawn from others but not sad?
 3 No change 2 Small Change 1 Medium Change 0 Large Change
6. Get confused or distracted more easily?
 3 No change 2 Small Change 1 Medium Change 0 Large Change
7. Have less ability to deal with frustration or stress?
 3 No change 2 Small Change 1 Medium Change 0 Large Change
8. Seem less concerned about the feelings of others than before?
 3 No change 2 Small Change 1 Medium Change 0 Large Change
9. Get angry or irritable more easily than before?
 3 No change 2 Small Change 1 Medium Change 0 Large Change
10. Seem more sarcastic or childlike than before?
 3 No change 2 Small Change 1 Medium Change 0 Large Change
11. Eat more or have a new preference for particular foods?
 3 No change 2 Small Change 1 Medium Change 0 Large Change
12. Have more trouble changing options or adapting to new situations?
 3 No change 2 Small Change 1 Medium Change 0 Large Change

13. Show less judgment or more problems making good decisions?

3 No change 2 Small Change 1 Medium Change 0 Large Change

14. Have less awareness of obvious problems or changes or deny them?

3 No change 2 Small Change 1 Medium Change 0 Large Change

15. Have new problems with language, such as saying the wrong word more?

3 No change 2 Small Change 1 Medium Change 0 Large Change

TOTAL SCORE:	  / 45
---------------------	-------------------------------

The following questions relate to current symptoms, not changes over time: Do you think your loved one:

1. Seems depressed on most days?

Yes No

2. Seems anxious on most days?

Yes No

3. Seems extremely fatigued on most days?

Yes No

4. Suffers from unexpected crying or laughing spells?

Yes No

APPENDIX 5. ALS Assessment Questionnaire 40 (ALSA-Q40)

ALSA-Q40

Please complete this questionnaire as soon as possible. If you have any difficulties filling in this questionnaire by yourself, please have someone to help you. However it is **your** responses that we are interested in.

The questionnaire consists of a number of statements about difficulties that you may have experienced **during the last 2 weeks**. There are no right or wrong answers: your first response is likely to be the most accurate for you. **Please check the box that best describes your own experience or feelings.**

Please answer every question even though some may seem very similar to others, or may not seem relevant to you.

All the information you provide is **confidential**.

The following statements all refer to difficulties that you may have had **during the last 2 weeks**. Please indicate, by checking the appropriate box, how often the following statements have been true for you.

The following statements all refer to certain difficulties that you may have had during the last 2 weeks. Please indicate, by checking the appropriate box, how often the following statements have been true for you.

*If you cannot walk at all
please check **Always/cannot walk at all**.*

How often during the last 2 weeks have the following been true?

Please check **one box** for each question

	Never	Rarely	Sometimes	Often	Always / cannot walk at all
1. I have found it difficult to walk short distances, e.g. around the house.					
2. I have fallen over while walking.					
3. I have stumbled or tripped while walking.					
4. I have lost my balance while walking.					
5. I have had to concentrate while walking					
6. Walking has worn me out.					
7. I have had pains in my legs while walking.					
8. I have found it difficult to go up and down the stairs					
9. I have found it difficult to stand up.					
10. I have found it difficult to move from sitting in a chair to standing upright.					

Please make sure that you have checked **one box for each question** before going on to next page.

The following statements all refer to certain difficulties that you may have had during the last 2 weeks. Please indicate, by checking the appropriate box, how often the following statements have been true for you.

*If you cannot do the activity all
please check **Always/cannot do at all**.*

How often during the last 2 weeks have the following been true?

Please check one box for each question

	Never	Rarely	Sometimes	Often	Always / cannot do at all
11. I have had difficulty using my arms and hands.					
12. I have found turning and moving in bed difficult.					
13. I have had difficulty picking things up.					
14. I have had difficulty holding books or newspapers, or turning pages.					
15. I have had difficulty writing clearly.					
16. I have found it difficult to do jobs around the house.					
17. I have found it difficult to feed myself.					
18. I have had difficulty combing my hair or brushing and/or flossing my teeth.					
19. I have had difficulty getting dressed.					
20. I have had difficulty washing at the bathroom sink.					

Please make sure that you have checked **one box for each question** before going on to next page.

The following statements all refer to certain difficulties that you may have had during the last 2 weeks. Please indicate, by checking the appropriate box, how often the following statements have been true for you.

If you cannot to do the activity at all
please check **Always/cannot do at all**.

How often during the last 2 weeks have the following been true?

Please check **one box** for each question

	Never	Rarely	Sometimes	Often	Always / cannot do at all
21. I have had difficulty swallowing.					
22. I have had difficulty eating solid food.					
23. I have had difficulty drinking liquids.					
24. I have had difficulty participating in conversations.					
25. I have felt that my speech has not been easy to understand.					
26. I have stuttered or slurred my speech.					
27. I have had to talk very slowly.					
28. I have talked less than I used to do.					
29. I have been frustrated with my speech.					
30. I have felt self-conscious about my speech.					

Please make sure that you have checked **one box for each question** before going on to next page.

The following statements all refer to certain difficulties that you may have had during the last 2 weeks. Please indicate, by checking the appropriate box, how often the following statements have been true for you.

How often during the last 2 weeks have the following been true?

Please check **one box** for each question

	Never	Rarely	Sometimes	Often	Always
31. I have felt lonely.					
32. I have been bored.					
33. I have felt embarrassed in social situations.					
34. I have felt hopeless about the future.					
35. I have worried that I am a burden to other people.					
36. I have wondered why I keep going.					
37. I have felt angry because of the disease.					
38. I have felt depressed.					
39. I have worried about how the disease will affect me in the future.					
40. I have felt as if I have lost my independence.					

Please make sure that you have checked **one box** for each question

Thank you for completing the questionnaire

ALSA-Q40 © Isis Innovation Limited, 2000. All rights reserved. Translated from English (UK) to English (USA) by Oxford Outcomes Ltd.

1 INTRODUCTION

This Statistical Analysis Plan (SAP) is based on Clinical Study Protocol (CSP) Version 2.0, dated May 5th, 2016, and the SAP of the IG1309 study.

Amyotrophic Lateral Sclerosis (ALS) is an adult-onset paralyzing, rapidly progressive neurodegenerative disease that affects the upper and lower motor neurons. It is characterized by the loss of motor neurons in the cerebral cortex, brainstem and anterior horn of the spinal cord. ALS manifests itself with motor deficits, muscle atrophy, and difficult in breathing, and it is often accompanied by difficulty in swallowing.

ALS is the motor neuron disease with the worst prognosis, with an average survival after diagnosis that falls between 2 and 5 years, and 60% of patients dying within the 3 years (1,2). Death of ALS patients is usually produced by respiratory failure (3).

Two types of ALS are predominantly distinguished by their onset: limb-onset ALS which begins with motor impairments of the extremities, and bulbar-onset ALS with motor impairments at the level of the cranial nerves (4).

ALS continues to be a devastating neurodegenerative disease with an uncertain pathogenesis, for which no cure exists. There have not been any precise biomarkers identified for the disease, and diagnosis is established through clinical manifestations and neuronal damage evaluated through electromyography (EMG).

Current treatment for this disease is related to excitotoxicity control, which has limited results with regard to the prognosis (5). The first drug approved for its treatment is Riluzole, a glutamate release inhibitor, which lengthens life expectancy by 2 to 4 months in patients with moderate functional impairment (6-7). More recently Radicava® (edaravone) was approved by FDA in 2017 and is the only new FDA-approved treatment option for ALS in the last 20 years shown to slow disease progression (8). It is a free radical scavenger, although the precise mechanism is unknown (9). Accordingly, the majority of interventions aimed at delaying the progression of the disease are at the symptomatic and/or palliative level. In this sense, care which helps preserve the quality of the subject's life is especially important and is mainly achieved via respiratory and nutritional support (10).

Among the clinical studies performed throughout the last 30 years, there were 3 pilot studies, which took place in the early 1980s, using plasmapheresis (a technique by which the plasma is separated from the formed blood components and discarded, and the components then returned to the subject) in a small number of ALS patients (11,12,13).

These studies made it possible to affirm that PE procedures are well tolerated by ALS patients. Nevertheless, they were not able to demonstrate efficacy due in part to methodological limitations that could be mitigated now, more than 30 years later, by using current knowledge of the disease and the experience acquired in ALS.

More specifically, some of the recruitment parameters used in the clinical design have been standardized (e.g., only including subjects having less than 18 months of disease progression and forced vital capacity (FVC) >70%) or the use of the ALSFRS-R functional scale as an efficacy variable.

The efficacy and safety of the plasmapheresis-based procedures have also improved, and their use has been expanded to numerous indications (14,15).

Instituto Grifols S.A. is currently studying the use of PE with Albutein in Alzheimer's disease (16). The working hypothesis stipulates that PE with albumin may change the metabolic profile

in ALS patients in both plasma and CSF; and in the case of CSF, this is thought to occur by altering the dynamic equilibrium between compartments. Thus, the potential benefits of PE may be due to the combination of the withdrawal of disease-inducing substances and to albumin's antioxidant effects and detoxifying functions via the transport and elimination of known and unknown harmful compounds. Furthermore, the study seeks to increase knowledge of potential new biomarkers for ALS.

However, disease progression has been found to be highly variable and does not always follow a linear descent (17,18). Therefore, the treatment will be considered efficacious when a subject's rate of decline is lower than the expected decline or disease progression assessed by ALSFRS-R.

For all these reasons, this pilot study was proposed with the objective of treating 10 ALS-diagnosed subjects, with PE using Albutein 5%.

Since ALS is a rapidly progressive disease, we plan to combine a first Intensive Treatment Phase followed by a Maintenance Treatment Phase in accordance with the progressive nature of the disease with the objective of obtaining disease stabilization or improvement.

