6.2.2. Baseline Visit (V0)

The Baseline Visit will extend through a maximum of 3 weeks. It will include the signing of informed consent, obtaining baseline parameters to assess subject's eligibility, and implementation of the necessary evaluations to obtain baseline parameters for the study variables. Given this window of 3 weeks for the Baseline Visit, Week 0 will be defined as the week immediately prior to when the first PE is performed allowing all other visits to be subsequently scheduled.

An initial visit will take place to explain the objective of the study and to give all the information to the subject so that the informed consent may be obtained.

A peripheral venous access assessment will be performed at the DHMC facilities, and a blood draw will take place to obtain a sample sufficient to perform the required laboratory tests. Blood samples will be taken when the subject has been fasting for a minimum of 4 hours:

- Safety Laboratory Analyses (analysis on site):
 - Coagulation: prothrombin time (PT), and activated partial thromboplastin time (aPTT)
 - Fibrinogen
 - Complete Blood Count: hematocrit, hemoglobin, erythrocytes, platelets, and leucocytes
 - Biochemistry + Lipid Profile: alanine transaminase (ALT), aspartate transaminase (AST), creatine kinase (CK), creatinine, ferritin, glucose, protein (pre-albumin, albumin, total protein in serum) and total cholesterol, high-density lipoprotein (HDL), low-density lipoprotein (LDL), and triglycerides
 - Serum Electrolytes: calcium, phosphate, sodium, potassium, chloride, and bicarbonate
 - Serology: HIV 1 & 2, HCV antibodies, and HBsAg antigen
 - Serology Retention Sample: retention samples taken and stored at -80°C

Additionally, a sample will be collected for baseline measurements of different biomarker parameters:

- Plasma Biomarkers (samples will be stored at -80°C):
 - Cytokine panel: human Apolipoproteins (ApoE2, ApoE3, and ApoE4), transforming growth factor beta (TGFβ1, 2, and 3), Interferon gamma (IFN-γ), interleukins IL-1β, IL-6, IL-10, IL-12p70, IL-17A, IP-10, MCP-1, MDC, MIP-1α, MIP-1β, tumor necrosis factor alpha (TNF-α), sCD40L, and fractalkine
 - Neurofilament analysis: phosphorylated neurofilament heavy chain (pNF-H) and neurofilament light chain (NF-L)
 - BMAA analysis: BMAA, L-Serine and amino acid profile
 - Biomarker retention samples: additional samples will be stored for future biomarker research

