3.3 Determination of sample size

There has been no formal calculation for the sample size since this is a pilot study. The number of subjects planned to be included in this study is 10 subjects completing the planned treatment. The sample size is considered adequate for the evaluation of the objectives of the study. In addition, there is a rising consensus in the ALS field that active control group comparisons should be avoided in early trials (19).

Lastly, the current EMA guidance document, *Guideline on clinical investigation of medicinal products for the treatment of amyotrophic lateral sclerosis (ALS) (EMA/CHMP/4015/2013)* states that the average functional decline is about 1 point per month in untreated subjects on the ALSFRS-R Functional Scale (20). Thus, it may be assumed that 10 subjects followed during 1 year of the clinical trial would be sufficient to evaluate a change of disease progression rate. In the event that a move towards stabilization is observed, the subsequent confirmatory studies will require a formal calculation for the sample size.

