4 EFFICACY AND SAFETY VARIABLES

4.1 Primary efficacy variable

- Changes from baseline in the ALSFRS-R Functional Scale (5 post-baseline measurements: Weeks 4, 12, 25, 36, and 48),
- Changes from baseline in the FVC (5 post-baseline measurements: Weeks 4, 12, 25, 36, and 48).

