6.3 Hypotheses and statistical methods

6.3.1 Summary statistics

Data will be presented using summary statistics.

All categorical variables will be summarized in frequency and percentage.

The continuous variables will be reported by sample statistics: n (number of observations), number of missing data, mean, standard deviation (SD), minimum, first quartile (Q1), median, third quartile (Q3), and maximum. The 95% Confidence Interval for the mean will be added for the primary and secondary efficacy variables, as well as p-value for test comparisons when necessary (see sections 6.3.4 and 6.3.5 for details).

The number of digits behind the decimal point will be 1 in tables with percentages.

The summary statistics minimum and maximum will be presented to the same number of decimal places as that used to collect the data, while mean, median, Q1 and Q3 will be presented to one more decimal places, and standard deviation will be presented to two more decimal places.

All the analysis will be performed using SAS® Enterprise Guide system version 7.11.

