6.3.4 Primary efficacy analysis

The primary efficacy analyses will be carried out on the evaluable population, and will also be performed using the PP population.

For the primary efficacy variable, the ALSFRS-R Functional Scale, in addition to the overall score, values of the different individual questions, and functional subdomains will be summarized by visit.

For all these variables, and for the co-primary efficacy variable, FVC, changes from baseline will be summarized by visit.

Differences between baseline and subsequent visits for the ALSFRS-R overall and for the bulbar, fine/gross motor and respiratory subdomains will be analysed using the student t-test (normal distribution) or nonparametric Wilcoxon signed-rank test. Comparison between ALSFRS-R Overall change from baseline values obtained versus expected ALSFRS-R Overall change from baseline values according to EMA guideline, i.e. decrease of 1 point by month, will be analysed using the one-sample student t-test in the cases where the assumptions of normality are met, or nonparametric Wilcoxon signed-rank test if not.

Differences between baseline and subsequent visits for the Forced Vital Capacity (FVC), in liters and percentage will be analysed using the student t-test (normal distribution) or nonparametric Wilcoxon signed-rank test.

ALS Functional Rating Scale – Revised (ALSFRS-R):

This test is a validated rating instrument for progression of disability in ALS that provides an estimate of the degree of the subject's functional impairment through a short questionnaire. The ALSFRS-R includes 12 questions to assess the level of self-sufficiency of subjects in various functional domains. Aspects of nourishment, personal care, personal autonomy, and communication are also evaluated. Each task is graded on a five point scale from 0 (not able to do) to 4 (normal ability). Individual scores are totaled to produce a final result of between 0 (worst) and 48 (best).

ALSFRS-R will be classified as following, between 3 subdomains:

- Bulbar function (questions #1 to #3),
- Fine and gross motor function (questions #4 to #9),
- Respiratory function (questions #10 to #12).

Note: item #5 (cutting food) is divided into 2 sub-items: #5a (without gastrostomy) and #5b (with gastrostomy). Only one of them can be filled, and the other one should be missing.

In case of any item is missing, the total score and the corresponding subdomain score will be considered missing.

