6.3.10 Definitions

1. Age

Age of the subject will be defined in years, as:

$$\text{Age} = \frac{(\text{date of informed consent signed} - \text{date of birth} + 1)}{365.25}$$

2. Time since diagnosis

Time since diagnosis will be reported in months, as the period of time between diagnosis date to the date of informed consent signed.

$$\text{Time since diagnosis} = \frac{(\text{date of informed consent signed} - \text{diagnosis date} + 1)}{30.4375}$$

3. Baseline and Change from baseline

Baseline will be defined as the measurement taken at the Baseline visit or the last measurement taken prior to the start of the study treatment (i.e. PE#1) if the parameter is not measured at the Baseline visit or there are multiple observations for the parameter at the Baseline visit.

Change from baseline values will be reported as the difference between: value at the visit minus value at baseline visit.

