6.4 Level of significance, multiple comparisons and multiplicity

If applicable, all statistical tests will be 2-sided and will be performed using a 5% significance level.

No adjustment for multiple comparisons or corrections for multiplicity are planned.

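### The only stated definition of efficacy compares a single subject's decline with a population average, so about half of subjects would meet it with no treatment effect; it is not linked to the planned group test or to one visit.

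*SAP*

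**What the plan says.** Protocol 1.2 and SAP 1 carry the same sentence: the treatment counts as efficacious when a subject's "rate of decline is lower than the expected decline or disease progression assessed by ALSFRS-R". It gives no number of subjects, visit, margin or confidence level. Just before it, both introductions describe progression as highly variable and not always linear.

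The benchmark is a population figure. SAP 3.3 cites the EMA guideline for an "average functional decline is about 1 point per month in untreated subjects on the ALSFRS-R Functional Scale"; Protocol 1.2 and 4.3 say the same.

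SAP 6.3.4 separately plans a one-sample t-test, or a Wilcoxon signed-rank test if normality fails, against the "expected ALSFRS-R Overall change from baseline values according to EMA guideline, i.e. decrease of 1 point by month". The variable has "5 post-baseline measurements: Weeks 4, 12, 25, 36, and 48" (SAP 4.1). SAP 6.3.1 adds: "The 95% Confidence Interval for the mean will be added for the primary and secondary efficacy variables". SAP 6.4 sets two-sided 5% tests and states: "No adjustment for multiple comparisons or corrections for multiplicity are planned".

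On time, SAP 6.3.10 divides days by 30.4375, but only for one variable: "Time since diagnosis will be reported in months". Protocol 6.2.2 states: "The Baseline Visit will extend through a maximum of 3 weeks". The schedule in Protocol 6.2.1 places that visit at weeks -2 to 0.

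**The concern.** A variable quantity falls on the better side of its own average in roughly half of cases. A rule that calls this efficacy, subject by subject, credits the treatment with natural variation.

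The group test in SAP 6.3.4 asks the right question, but the efficacy sentence does not refer to it. The test itself leaves two choices open: which of the five visits decides, and how many months each visit represents.

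Protocol 11.5 says the 10 subjects are there to verify proof of concept, and Protocol 4.3 makes later confirmatory studies depend on a move towards stabilization. If the report follows the introductory sentence, slow progression by chance can be reported as efficacy. If it follows SAP 6.3.4, the deciding visit can be chosen after the data are seen.

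**Working it through.** The plan has no figure to reproduce: there is no SD, effect size, power or responder rate behind the 10 subjects.

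**Inputs from the documents.** n = 10 (SAP 3.3); benchmark 1 point per month (SAP 6.3.4); visits at weeks 4, 12, 25, 36 and 48 (SAP 4.1); two-sided 5%, no adjustment (SAP 6.4).

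**Assumptions.** No treatment effect; true mean decline 1 point per month; between-subject SD of the rate 0.5 to 0.9; residual SD 1.5 points on the change score; complete data. Rates are normal, gamma (right-skewed) or mirrored gamma (left-skewed).

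**1. Months at each visit.** m = weeks × 7 / 30.4375:

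| Week | 4 | 12 | 25 | 36 | 48 |
|---|---|---|---|---|---|
| Months | 0.92 | 2.76 | 5.75 | 8.28 | 11.04 |

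**2. Chance that one subject meets the sentence.** The change is -b·m + e, with b the subject's rate and e the residual. The sentence is met when the change exceeds -m, that is, when -(b - 1)·m + e > 0. If b is symmetric about 1 and e about 0, this probability is exactly 0.5. By simulation:

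| Rates | Week 25 | Week 48 |
|---|---|---|
| Symmetric | 0.50 | 0.50 |
| Gamma, SD 0.5 to 0.9 | 0.546 to 0.605 | 0.561 to 0.615 |
| Mirrored gamma, SD 0.5 to 0.9 | 0.454 to 0.395 | 0.440 to 0.385 |

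Week 4 differs. The benchmark loss is 0.92 points and scores are whole points, so only a subject with no net loss qualifies: 0.39 to 0.41.

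A separate run used whole-point scores throughout, rate SD 0.5 to 1.0 and measurement SD 0 to 2. For weeks 25 to 48 it gave 47 to 53% with normal rates and 50 to 68% with gamma or lognormal rates. For week 4 it gave 15 to 45%.

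**3. Number out of 10.** With p = 0.5 the expected count is 5. P(at least 1) = 1 - 0.5^10 = 0.999; P(at least 5) = 0.623; P(at least 6) = 0.377. With the lowest p above, 0.385, P(at least 1) = 1 - 0.615^10 = 0.992.

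**4. Five group tests, no decisive visit.** One two-sided 5% test has a nominal 2.5% chance of a favourable result under the null. Five independent tests would give 1 - 0.975^5 = 0.119. Visits share subjects, so the simulated figure for normal rates is lower: 0.060 to 0.070 if part of the residual is a shared baseline error, 0.069 to 0.085 if errors are independent. With gamma rates it is 0.100 to 0.126 and 0.117 to 0.140, because the t-test is itself off its nominal level for skewed data at n = 10.

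**5. Month conversion.** Taking week 48 as 12 months instead of 11.04 makes the benchmark loss 12 - 11.04 = 0.96 points larger, hence too lenient. A baseline score taken 14 days early, with nominal weeks used, omits 14 / 30.4375 = 0.46 months, which makes the benchmark 0.46 points too strict.

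**6. A single week-25 rule (95% CI wholly above -1 point per month).** Under the null it is met in 2.3 to 2.6% of trials with symmetric rates and 4.1 to 7.5% with gamma rates. If mean decline halves to 0.5, the SD of a subject's monthly change at rate SD 0.5 is √(0.5² + (1.5/5.75)²) = 0.564. The noncentrality is 0.5 × √10 / 0.564 = 2.80, and power with 9 df is 0.70. At SD 0.7 and 0.9 it is 0.47 and 0.33. With gamma rates halved, power is 0.95, 0.85 and 0.75.

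**7. Descriptive count.** The exact 95% CI for 5 of 10 is 18.7 to 81.3%.

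**The case against.** The strongest reply is that the sentence is background. It stands only in the rationale and introduction, and no endpoint, analysis section or planned table counts subjects slower than 1 point per month. Protocol 11.2 calls the evaluation descriptive, and SAP 6.3.4 already turns the expected decline into a group test with a CI. On that view only a cross-reference and a named visit are missing. It is true that the group test is sound and that the harm depends on which text the report follows. But this is the only statement of when the treatment is efficacious, it is worded as a decision rule, and it was carried into the final SAP beside tests at 5%.

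The words about disease progression could mean the subject's own earlier course, since Protocol 6.2.2 collects ALSFRS-R values from the previous six months where possible. The SAP only describes, plots and lists those values. With steady decline and no effect, about half would be expected to beat their own past rate too. This reading adds ambiguity and supplies no criterion.

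The sizes do depend on assumptions. If trial subjects truly decline at 0.7 or 1.3 points per month without an effect, the share at weeks 25 to 48 becomes 63 to 77% or 33 to 43% (rate SD 0.75, measurement SD 1). Riluzole users may enrol, while the benchmark is for untreated subjects. The at-least-one-of-ten figure describes a rule that no passage states.

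On months, no passage says the test will take week 48 as 12 months. However, the documents equate 24 weeks with six months, and SAP 3.1 describes a 12-month study, so that reading is available.

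**Conclusion.** The concern holds and should be fixed. Followed as written, the efficacy sentence would label about half of subjects as showing efficacy at the later visits with no treatment effect: exactly 50% for symmetric rates centred on the benchmark, more with right skew, less with left skew. This rests on untreated trial subjects averaging 1 point per month. The SDs and shapes are assumptions, and complete data are assumed throughout.

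The group test in SAP 6.3.4 would be an adequate basis, but it is not named as the criterion. With five unadjusted visits its favourable false-positive rate is roughly two to six times the nominal 2.5%. The month conversion can move the week-48 benchmark by up to about one point. Confidence is high about the missing criterion and lower about the exact percentages.

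**What to change.** In Protocol 1.2 and SAP 1, replace the sentence with a group-level criterion that refers to SAP 6.3.4, for example:

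> Evidence of slowing requires the two-sided 95% confidence interval for the mean monthly ALSFRS-R change from baseline to Week 25 to lie wholly above -1.0 point per month.

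Week 25 is the first ALSFRS-R assessment after treatment ends. If the sponsor prefers another visit, it should be named before the data are analysed. In SAP 6.3.4:

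- treat the other four visits as supportive;
- compute each subject's months as actual days since the baseline ALSFRS-R divided by 30.4375;
- report the number of subjects slower than 1 point per month descriptively only, with an exact binomial CI;
- state how subjects without a score at the named visit are handled, since SAP 6.6 plans no imputation.

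The cost is one sentence in each document, short additions to SAP 6.3.4 and one derived variable; the CI and the test are already planned. The claim becomes harder to meet: if decline halves, the week-25 rule is met in 33 to 71% of trials with symmetric rates, or 75 to 95% with gamma rates. For 30% slowing, a calculation without measurement error gives 40, 20 and 13% at rate SD 0.5, 0.75 and 1.0.

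The rule does not cure everything. Its null error stays above 2.5% under right skew: 4 to 7.5% with gamma rates and about 10% in one lognormal run at SD 0.75. The benchmark remains external, and FVC still has no criterion. The result therefore remains pilot evidence.
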